### Objectives

- Primary objective: To evaluate the tolerability of tDCS in childhood stroke survivors.
  - Tolerability will be evaluated by
    - The percent of patients who are able to complete the study
    - The percent of patients that endorse mild side effects as documented on the 'Stimulation Monitoring Sheet' (included separately)
    - Monitoring of Peg-Board test results pre stimulation, post stimulation, and at the end therapy session
    - Monitoring of Vital Signs (pulse and blood pressure) pre stimulation, post stimulation, and at the end of the therapy session.
- Secondary Objectives: To assess for improvement in arm function in patients receiving tDCS and occupational therapy, 3 functional assessment visits will take place.
  - At each visit, the patient will complete the following:
    - Fugl-Meyer Upper Extremity Assessment
    - Canadian Occupational Performance Measure
    - Box and Blocks Test
    - Pediatric Stroke Outcome Measure
    - Melbourne Assessment of the Upper Extremity

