### Outcome Measures:

- Tolerability Primary outcome measure:
  - Percent of patients who complete the study, as defined by patients who complete the 1-week post therapy assessment visit. Patients who voluntarily withdraw for any

- reason or who stop due to an adverse event will be defined as not completing the study.
- Tolerability Secondary outcome measures
  - Percent of patients that endorse mild side effects as documented on the stimulation monitoring sheet. The stimulation monitoring sheet is filled out during each stimulation session pre and post stimulation.
  - Percent of patients with hypotension or hypertension on blood pressure monitoring post stimulation and post therapy session. Time points for data collection will be pre-stimulation, post-stimulation, and post-therapy session.
  - Percent of patients with worsening of the Peg-board test (decreased score by 5 or greater) on the Peg-Board Test post stimulation and at the end of therapy session compared to baseline score. Time point will be the end of each therapy session.
- Improvement in Arm Function Primary outcome measure
  - Increase of 5 points or more on the Fugl-Meyer score of Upper extremity function at the 1 week post therapy assessment.
- Improvement in Arm Function Secondary Outcome Measure
  - Increase of 5 points or more on the Fugl-Meyer score of upper extremity function at the 3 month post therapy assessment.

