### **Study Population**

Patients to be enrolled will be childhood stroke survivors aged 5-19 yrs. 'Childhood' stroke is defined by the American Heart Association as stroke occurring from 29 days of life to 18 years of life.

– **Inclusion Criteria:**

- 1) Childhood stroke survivor - either arterial ischemic stroke or intracerebral hemorrhage.
- 2) Stroke must be childhood onset, defined as occurring day 29 of life to 18 years of age (per the American Heart Association's definition of childhood stroke)
- 3) 3 months or greater from stroke onset
- 4) Arm impairment, defined as pediatric stroke outcome measure of 1 or greater of affected arm.
- 5) Affected arm Fugl-Meyer score of 60 or lower.
- 6) Able to participate in occupational therapy sessions.

– **Exclusion Criteria:**

- 1) Uncontrolled epilepsy, defined as seizure within the past 6 months.
- 2) Craniectomy without replacement of bone flap. Patients who underwent craniectomy will need the bone flap reattached prior to participation.
- 3) Presence of cranial metal implants or implant device that could be affected by tDCS: cochlear implant, implanted brain stimulator, or programmable ventriculoperitoneal shunt.

Patients will be identified in the UTHealth Pediatric Stroke clinic by the PI, [name]. Flyers for the study will also be available on the UTHealth website. The flyer is included in the study documents.

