### **Study Procedures**

- There will be 3 assessment visits and 5 therapy visits.
- Baseline assessment visit: This visit will take approximately 2 hours. A study physician will fill out the 'medical history' form and complete the Pediatric Stroke Outcome Measure
  - The Pediatric Stroke Outcome Measure is a standardized neurologic exam used for childhood stroke survivors.

- The therapist will complete 4 tests:
  - 1) Fugl-Meyer test, a 30 minute therapy evaluation tool to assess arm function
  - 2) The Canadian Occupational Performance Measure, a structured interview to assess activities of daily living
  - 3) The Box and Blocks test – a two minute test of hand dexterity in which the subject moves blocks from one area to another while remaining seated.
  - 4) Melbourne Assessment of the Upper Extremity, a 30 minute unilateral assessment of the affected arm.
- 5 occupational therapy sessions. These will take approximately 2 hours each.
- The 2 follow up assessments are done at 1 week and 3 months post intervention. Each which will take 1-2 hours. A study physician will perform the Pediatric Stroke Outcome Measure, and the study therapist will perform the Fugl-Meyer test, the Canadian Occupational Performance Measure, Melbourne Assessment of the Upper Extremity and the Box and Blocks test.

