### **Statistics**

- As this is a 5 patient tolerability study, only descriptive statistics will be used.
- 5 patients total will be enrolled, and results will be reported with descriptive statistics.
- The trial will be terminated if there is a major safety event deemed to be due to the intervention by the DSMB.
- All subjects will be included in the descriptive analysis.

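### Both arm-function outcomes are a yes/no Fugl-Meyer gain of 5 or more points with no stated reference visit, and the four companion scales have no planned summary

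*Combined protocol and SAP*

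**What the plan says.** The Outcome Measures section of the combined protocol and SAP gives arm function two outcomes. The primary one is "Increase of 5 points or more on the Fugl-Meyer score of Upper extremity function at the 1 week post therapy assessment". The secondary one is "Increase of 5 points or more on the Fugl-Meyer score of upper extremity function at the 3 month post therapy assessment". Neither states the reference visit, and neither mentions a change score, a median or mean, a listing by child, or a source for the 5-point threshold.

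Arm function is a secondary objective of the trial. The Objectives section says: "To assess for improvement in arm function in patients receiving tDCS and occupational therapy, 3 functional assessment visits will take place". It then lists five scales for each visit: Fugl-Meyer, COPM, Box and Blocks, PSOM and Melbourne. Study Procedures confirms that all five are repeated at 1 week and 3 months, with a physician doing the PSOM and the therapist doing the other four. Only the Fugl-Meyer appears among the arm-function outcomes.

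The Statistics section adds that "5 patients total will be enrolled, and results will be reported with descriptive statistics" and that "All subjects will be included in the descriptive analysis". It does not say which quantities will be described.

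**The concern.** A cut at +5 puts a child who gains 4 points and a child who loses 10 in the same class. In a five-child study without a control arm or any test, the description is the whole arm-function result, so the choice of what to describe matters.

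The same section handles the Peg-Board test more carefully: it gives that test a definition of worsening (a drop of at least 5) and names baseline as the comparator. The Fugl-Meyer outcomes have neither.

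The four other scales raise a related problem. With no planned summary, the authors can choose after seeing the data which scale, which follow-up visit and which direction of change to report.

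A smaller point concerns the denominator. Outcome Measures defines completing the study as attending the 1-week visit, and that visit is also the source of the 1-week Fugl-Meyer score. A child who does not complete therefore has no 1-week score, and the plan gives no rule for including that child among all subjects.

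**Working it through.** The plan contains no sample-size, power or effect-size figure for arm function, so there is none to reproduce.

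**Inputs from the documents:** n = 5, one arm (Study Design, Statistics); threshold of +5 Fugl-Meyer points at 1 week and 3 months (Outcome Measures).

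**Inputs assumed:** a normally distributed change score, with mean 0 to 5 points and SD 2 to 6 points. The documents give neither figure.

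**1. What the count can show.** Taken as a share of five children, the outcome has six possible values: 0, 20, 40, 60, 80 and 100%. Two invented sets of changes show what it hides:

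| Changes | Improved (5 or more) | Mean | Median |
|---|---|---|---|
| 4, 4, 4, 4, 5 | 1 of 5 | 21/5 = 4.2 | 4 |
| -3, -2, 0, 1, 5 | 1 of 5 | 1/5 = 0.2 | 0 |

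This step needs no distributional assumption.

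**2. Information kept after the cut.** For a normal variable with known SD and responder rate p, the share of information on the mean that survives is φ(c)² / [p(1 − p)], where c is the standard normal quantile of p.

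- p = 50%: c = 0, 0.3989² / 0.25 = 0.637. Kept 64%, lost 36%; this is the best case.
- p = 20% or 80%: 0.49 kept.
- p = 10% or 90%: 0.34 kept.
- The share kept falls to one half at p = 20.9%, and by symmetry at 79.1%.

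**3. Range over the assumed means and SDs**, with p = P(change ≥ 5):

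- Mean 4, SD 4: p = 40%, 62% kept.
- Mean 2, SD 4: p = 23%, 52% kept.
- Mean 2, SD 3: p = 16%, 44% kept. The chance that no child of five reaches +5 is (1 − 0.159)^5 = 42%.
- Extremes of the grid: 5% kept (mean 0, SD 2) and 64% kept (mean 5, any SD).

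**4. Denominator.** If two children improve and one of the others misses the visit, the result is 2/5 = 40% or 2/4 = 50%, depending on a rule the plan does not give.

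**The case against.** The strongest reply is that this is a tolerability study, that arm function is secondary, and that no test, interval or decision depends on the 5-point cut. The information formula concerns the precision of an estimated mean, which the plan does not set out to estimate formally. The tolerability outcomes are each worded as a percentage of patients, whereas the arm-function ones are not, so reporting them as a responder share is itself an inference. Nothing in the Statistics section forbids showing raw scores.

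Much of this stands, and it limits the weight of the point. It does not remove it. The only definition of improvement in the plan is the cut, and the general reference to descriptive statistics commits to no change score. Where a further summary was intended, as for the day-1 sham data in Study Design, the plan says so. The two-set example above holds without the formula.

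A reader might infer more than the documents support:

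- *That the cut discards most of the information.* That depends on a responder rate the documents do not give. At rates between about 21% and 79%, more than half is kept.
- *That the other four scales are unused.* They are listed under the arm-function objective, and the PSOM also sets eligibility. What is missing is an outcome measure or summary.
- *That the study cannot show harm to the arm.* The Attachments section places the Fugl-Meyer forms inside the case report form, and Data and Safety Monitoring sends that form to the DSMB after the 1-week visit, before the next child starts the intervention. The Peg-Board outcome also looks for motor worsening.
- *That a ceiling makes the cut unreachable for mildly affected children*, given the entry criterion "Affected arm Fugl-Meyer score of 60 or lower". The documents do not give the scale maximum, so no such figure can be supported.

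It is also fair to say that a change score does not cure a missed visit. The count needs its own rule, and the listing should show the gap.

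**Conclusion.** The point holds as a gap in the planned outcome. As written, a child with a small gain and a child with a decline receive the same classification, the reference visit is left to be presumed, and four collected scales have no stated summary. The same result of 1 of 5 can go with a mean change of 4.2 or 0.2 points. The loss of information is at least 36% under assumed normality; any larger figure depends on an assumed mean and SD.

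The consequences are modest. The primary tolerability result is unaffected, no inference rests on the cut, and the individual scores are captured. This is a cheap improvement, and nothing here invalidates the study.

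**What to change.** In Outcome Measures, make change from baseline in Fugl-Meyer points, at 1 week and at 3 months, the arm-function outcome, and name the baseline assessment as the reference. In Statistics, commit to a table listing each child's baseline score, follow-up scores and changes, decreases included, with the median and range.

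Keep the 5-point gain as a supporting count out of all treated children. Show a child without the visit as missing in the listing and count that child as not improved.

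Give the same listing for the COPM, Box and Blocks, Melbourne and PSOM, labelled exploratory, and state for each which direction is improvement.

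The cost is a few sentences and one more table, with no new visits or data. The price is a less simple headline than a single count.

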### **Study Design**

- This study is an unblinded interventional trial.
- Subjects will be childhood stroke survivors with chronic arm impairment, defined below in the inclusion and exclusion criteria. 5 patients total will be enrolled.

The Primary Objective is to assess tolerability of tDCS. Tolerability will be evaluated by

- The percent of patients who are able to complete the study
  - If any patients drop out due to tDCS related side effects, this would be considered poorly tolerated.
- The percent of patients that endorse mild side effects as documented on the 'Stimulation Monitoring Sheet' (included separately)
  - We expect 40% of patients to endorse mild side effects per session that will be non-treatment limiting.
- Monitoring of Peg-Board test results pre stimulation, post stimulation, and at the end therapy session to ensure no decrease (worsening) in score poststimulation.
- Monitoring of Vital Signs (pulse and blood pressure) pre stimulation, post stimulation, and at the end of the therapy session.
- Study description and sample timeline:
  - On enrollment, patients will have a study visit where they will have a Pediatric Stroke Outcome Measure completed by the PI as well as a medical history with the enrollment form. The study therapist will then complete the following assessments – Fugl-MeyerScore, Canadian Occupational Performance Measure, Box and Blocks test, Melbourne.
  - The patient will then come for 5 sequential days of 2 hour long occupational therapy sessions augmented by tDCS for the first 20 minutes of the session. At arrival, the "stimulation safety sheet" will be completed by the occupational therapist (form attached). The saline soaked electrodes will be placed on the study subjects head and connected to the

Soterix 1x1 LTE enabled tDCS device. Prior to beginning stimulation, the "Investigator Screening Form" checklist will be completed for each patient during each stimulation. Current output through the device will be sham stimulation on day 1, followed by steady increases to a maximum of 1mA in patients aged 5-12 years old, and 1.5mA in patients aged 13-19 years old, per the study design flow sheet at the end of this protocol. The child and parents will be blinded to the sham stimulation. The investigators will not be, since all patients receive the same age based current protocol. Consequently, investigators will be aware it is sham stimulation on day 1. We have chosen to have sham stimulation on the first day to acquire baseline data for tolerability and reported side effects without current being passed through the electrodes, which we will report with descriptive statistics. Blood pressure, pulse rate, and peg-board scores will be recorded as indicated on the stimulation safety sheet during each session.

- A repeat assessment will be done by the occupational therapist one week post therapy completion.
- There will be a repeat assessment visit 3 months post intervention.

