### **Data and Safety Monitoring**

- No major adverse events are expected. We will monitor for hypotension, tachycardia, and mild side effects like headache. We expect about 40% of patients will endorse the expected mild side effects: headache, numbness or tingling. We expect no patients will develop hypotension or tachycardia.
- If any patient does have a major adverse event, the intervention will be stopped, the event will be logged on the case report form and the patient will be given all usual emergency medical care. The event will be sent to the Data Safety Monitoring Board who will independently review the event and decide whether the event was caused by the intervention. If it is, the study will be discontinued and the protocol revised.
- There is a two person Data Safety Monitoring Board. Case Report Forms for all participants will be sent to the DSMB electronically after completion of the 1st follow up assessment visit (1 week post intervention) for review. The DSMB will need to approve that the study can continue prior to beginning the intervention for the next patient.

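### Does the percentage of children with mild side effects need a stated counting window over the five sessions?

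*Combined protocol and SAP*

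**What the plan says.** The Outcome Measures section lists, among the secondary tolerability outcomes, "Percent of patients that endorse mild side effects as documented on the stimulation monitoring sheet". The next sentence gives the recording schedule: "The stimulation monitoring sheet is filled out during each stimulation session pre and post stimulation". It gives no rule for combining sessions.

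The Study Design section names the same measure and the same sheet, and directly beneath it states "We expect 40% of patients to endorse mild side effects per session that will be non-treatment limiting". Each child attends "5 sequential days of 2 hour long occupational therapy sessions augmented by tDCS". Day 1 is sham, included to obtain "baseline data for tolerability and reported side effects without current being passed through the electrodes, which we will report with descriptive statistics".

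The Data and Safety Monitoring section says "We expect about 40% of patients will endorse the expected mild side effects: headache, numbness or tingling", with no time basis. The Statistics section limits the analysis to descriptive statistics on all five subjects.

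**The concern.** A percentage of patients taken over repeated sessions needs a window. A child who reports tingling on one day out of five is a case if the window is the whole course, and a case on one day only if the window is the session. The Outcome Measures section says when the sheet is completed but not which of these is meant. The expectation appears once per session and once with no basis, so a reader might set a whole-course result against a per-session 40% and conclude that stimulation was less well tolerated than expected.

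Two features sharpen the worry. Day 1 delivers no current and later days step up, so sessions are not interchangeable, and a whole-course figure that included day 1 would mix sham and active reports. Also, although Outcome Measures ranks this outcome as secondary, the Objectives and Study Design sections list it among the measures by which the primary objective, tolerability, is evaluated.

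**Working it through.** **Inputs.** Five children (Statistics). Five sessions (Study Design). Day 1 sham (Study Design). Expected 40% of patients per session (Study Design) and about 40% with no time basis (Data and Safety Monitoring). I assume that days 2 to 5 all deliver current, which gives four active sessions; the flow sheet that would confirm this is not shown.

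**The plan's own figure.** The 40% is a stated expectation with no derivation, so there is nothing to reproduce. In children it is 0.40 × 5 = 2 per session.

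**From per session to whole course.** Suppose exactly 2 of 5 children report at each active session.

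- Reports in total: 2 × 4 = 8 of 5 × 4 = 20 child-sessions, which is 40%.
- One child can supply at most 4 of these, so at least 8 / 4 = 2 children report at some time. At most all 5 do.
- Every value between is possible. With children A to E over days 2 to 5:

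| Who reports on days 2, 3, 4, 5 | Per session | Children ever reporting |
|---|---|---|
| AB, AB, AB, AB | 40% | 2 of 5 = 40% |
| AB, AC, AB, AC | 40% | 3 of 5 = 60% |
| AB, CD, AB, CD | 40% | 4 of 5 = 80% |
| AB, CD, AE, BC | 40% | 5 of 5 = 100% |

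With the sham day included, there are 2 × 5 = 10 reports in 25 child-sessions. At least 10 / 5 = 2 and at most 5 children report, so the bounds are again 40% and 100%.

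**From whole course to per session.** Suppose 2 of 5 children report at least once over the active days. If each reports once, the average per-session figure is 2 / 20 = 10%. If each reports every time, it is 8 / 20 = 40%. Over five sessions the limits are 2 / 25 = 8% and 10 / 25 = 40%.

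These are counting limits, not predictions. A point value between them would need a within-child correlation, which the documents do not give. The two counts agree when the same children report at every session.

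**What depends on the 40%.**

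- Sample size: five, with no calculation behind it.
- Tests: none, since the analysis is descriptive.
- Termination: tied in the Statistics section to a major safety event that the monitoring board attributes to the intervention.
- Tolerability judgement: "If any patients drop out due to tDCS related side effects, this would be considered poorly tolerated". This turns on dropout, not on the frequency of mild symptoms.
- Primary outcome: completion of the one-week assessment visit.

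None of these takes the 40%, or the observed mild-side-effect percentage, as an input.

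**The case for a change.** The strongest case for a change is that in a descriptive study the percentage is itself the result, so its definition matters even with no test attached. An expectation placed under a measure does not define it. The unqualified 40% could be a whole-course figure: the Background section cites 37% of patients with mild tingling or itching in an earlier pediatric series, also with no session basis. One sentence would settle the matter at almost no cost.

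Much of this stands. The Outcome Measures section does leave the window unstated, and a whole-course percentage should not be judged against a per-session 40%. It does not show, however, that following the plan would give a wrong result. Study Design ties the session to this very measure, and no section states a whole-course percentage or a whole-course expectation. The Data and Safety Monitoring sentence can be read as a shortened form of the same figure, so no contradiction is established. The paired entries before and after stimulation, with the promised sham-day report, already point to a sensible handling of background symptoms. The monitoring sheet is supplied separately and was not available; it may say more.

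Nor does the Peg-board outcome show that this one was singled out. Its statement, "Time point will be the end of each therapy session", is also a time of measurement repeated over five sessions, and it leaves the same choice between any session and each session open.

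**Conclusion.** No change to the plan is called for. The counting window is a missing detail that an analyst would fill in the ordinary way: report the number of children with symptoms at each session, keep day 1 apart as the sham baseline, and, if a whole-course count is given, label it as such. With five children and five sessions there are 5 × 5 × 2 = 50 before-and-after form completions at most, few enough to show in full, so neither reading need be hidden.

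The largest possible discrepancy is 40% against 100% for the same data, under exactly 2 of 5 reports at every session. It affects how one secondary descriptive figure is labelled and compared with an informal expectation. It does not affect the primary outcome, the dropout rule, termination of the trial or the sample size. The conclusion rests on the per-session wording in Study Design applying to the same measure, which its placement supports. The four-session arithmetic also assumes that days 2 to 5 are all active, though the 40% to 100% bounds are the same for five sessions.
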